1.4 PATIENT AND SAMPLE DISPOSITION

A detailed description of participant accountability including count of participants by analysis populations, screen failure participants with reasons for screen failure, participants who did not complete the study observation period along with the main reason for permanent treatment discontinuation, and participants who requested permanent treatment discontinuation, will be generated by cohorts.

All withdrawals from the study, taking place on or after study intervention intake, will be fully documented in the body of the clinical study report (CSR).

A listing of subjects with treatment discontinuation will be provided.

1.5 ANALYSIS POPULATIONS

Table 1 - Populations for analyses

Population	Description
Baseline biomarker	All participants who were enrolled in the study, who had a sample drawn for biomarker measurement and successfully analyzed at baseline.
Pharmacodynamic (PD)	All participants who were enrolled in the study, who had a sample drawn for biomarker measurement and successfully analyzed at baseline and at any post-baseline visit.

1.6 BIOMARKER ANALYSIS OBJECTIVES

The followings are the analysis objectives of biomarkers (lipidomics, proteomics, transcriptomics, FLG):

- Evaluate dupilumab treatment effect on skin biomarkers using STS samples in both predefined lesional and non-lesional skin in pediatric patients with moderate-to-severe AD during dupilumab treatment phase and follow-up period in reference to normal skin of healthy volunteers.
- Explore the association of skin barrier function measured by TEWL with disease impact assessed by standard AD severity assessments (EASI, and ISS), PRO (POEM, CDLQI, worst itch NRS, sleep disturbance NRS,)patient reported outcomes (PRO) (Patient Oriented Eczema Measure [POEM], Children Dermatology Life Questionnaire Index [CDLQI], worst itch Numerical Rating Scale [NRS], sleep disturbance NRS, skin pain NRS), standardized photos, the biomarker profiles of lipidomics, proteomics, FLG, and transcriptomics assessed in the STS samples, and the skin barrier hypertrophy and structure profiles assessed by OCT and FTIR.

1.7 BIOMARKER ASSESSMENTS AND SCHEDULE

1.7.1 Lipidomics, proteomics, and transcriptomics

Samples for skin lipidomic assessment are required and will be collected from all participants in this study.

Targeted skin lipidomics will be performed by means of a validated mass spectrometry method from skin tapes that have been collected during tape stripping at the TEWL assessment. The detailed assessment plan for lipidomics is listed in [Section 4.1.1](#).

Protein extracts will be prepared from STS samples by LC-MS/MS. The detailed assessment plan for proteomics is listed in [Section 4.1.2](#).

Skin tapes will be collected for transcriptomic analysis. The detailed assessment plan for transcriptomics is listed in [Section 4.1.3](#).

For both AD pediatric patients and healthy volunteers, samples are collected at Week 0, 2, 4, 8, 12, 16, and 22. All STS will be conducted on the predefined spots. TEWL will be assessed before STS and after 5, 10, 15, and 20 STS in lesional and non-lesional skin (AD patients) and normal skin (healthy volunteer). Weeks and spot on which STS is conducted are

- At Weeks 0, 8, 16, and 28, STS conducted on the first spot.
- At Week 2, STS conducted on the second spot.
- At Weeks 4, 12, 22, STS conducted on the third spot.

All skin tape strips should be collected and stored.

1.7.2 Optical coherence tomography (OCT)

OCT is a non-invasive imaging modality conceptually like ultrasound but uses near-infrared radiation rather than sound. The detailed assessment plan for OCT is in [Section 4.1.4](#). For both AD pediatric patients and healthy volunteers, samples for OCT are generated at Week 0, 1, 2, 3, 4, 6, 8, 12, 16, and 28. OCT will be done before STS/TEWL.

1.7.3 Attenuated total reflectance (ATR) FTIR spectroscopy

ATR FTIR spectroscopy is a form of molecular spectroscopy useful for the analysis of surfaces, including the lipid, water, and carboxylate content of the skin barrier and for analyzing lipid arrangement/structure. The detailed assessment plan for FTIR spectroscopy is in [Section 4.1.5](#). For both AD pediatric patients and healthy volunteers, samples for FTIR spectroscopy are generated at Week 0, 8, 16 and 28. FTIR will be done before and during STS.

1.7.4 Optional samples for biomarker research

The following optional serum and plasma samples for biomarker research should be collected from participants in the study, where possible. The detailed collection plan for optional samples is in [Section 4.1.6](#). For both AD pediatric patients and healthy volunteers, optional blood samples are collected at Week 0 and 16.

2 STATISTICAL AND ANALYTICAL PROCEDURES

2.1 PREPROCESSING AND QUALITY CONTROL

2.1.1 Data normalization

2.1.1.1 *Lipidomics*

STS samples processing for lipid extraction will be done as described in [Section 4.1.1](#). Lipidomic data will be provided as absolute concentration in pmol/mg protein or in ug/mg protein requiring no normalization step. Values below limit of quantification (LLOQ), missing values, and outliers will be treated as described in [Section 2.1.2](#).

2.1.1.2 *Proteomics*

There is no normalization step performed after sample analyses as specified by National Jewish Health (NJH). Polar metabolite samples will be normalized based on sample protein values before running the assay then signal intensities are expressed relative to healthy volunteers' group.

2.1.1.3 *Transcriptomics*

Raw sequencing data (fastq files) will be taken through successive steps to generate expression measures at gene level (counts): quality control, adapter trimming and filtering, mapping of reads to the human reference genome or pseudo-alignment to the transcriptome, quantification. These steps will be performed by NJH. The raw and the preprocessed transcriptomic data will be sent to Sanofi.

Samples filtering

Total RNA from the skin tapes will be normalized for cDNA generation and preparation of sequencing libraries. Both the cDNA and sequencing libraries generated will be quantified and qualified using the Bioanalyzer High-Sensitivity DNA chip. Samples that will yield low quality cDNA and sequencing libraries will not be sequenced.

Gene filtering

Genes having very low counts across all libraries will be filtered out. For this purpose, the count per million (cpm) values will be computed. Counts per million are counts scaled by the number of sequenced fragments in a sample (library size) times one million. Genes with less than 1 cpm in more than half of the samples will be filtered out. This filtering rule will be applied separately for count data matrices in HV and AD cohorts. Genes that successfully pass the filter in at least one data set will be kept. The specific threshold of 1 cpm may be adjusted depending on count distribution in the dataset.

Normalization and transformation of counts data

Normalization is a process designed to remove systematic technical differences between samples to ensure that technical bias has minimal impact on the results. One can envisage within-sample and between-samples normalization. In this study since we are interested in differential expression between experimental conditions rather than comparing expression of different genes in a sample, only a between-sample normalization will be performed. Using the DESeq2 R package, variance stabilizing transformation (VST) will be applied for analyses other than differential testing, for example clustering of samples or other machine learning applications. For differential testing the DESeq function will be applied to raw counts.

Included in VST, a log2 transformation is performed after addition of a small offset to avoid taking the log of zero. The quality of the normalization will be assessed by plotting the densities of variance-stabilized counts for the different samples. Since it is assumed that most of the genes are unaffected by the experimental conditions, a successful normalization should lead to overlapping densities. The mean-variance association will also be investigated before and after normalization. Samples boxplots will be plotted before and after normalization.

2.1.2 Missing data, outlier, and batch effect assessment

2.1.2.1 Data imputation

For each biomarker, the number of values below LLOQ will be computed by group (lesional, non-lesional and healthy skin). Values below LLOQ will be imputed according to the following rules:

- If for a given biomarker, less than 25% of all samples have values below LLOQ, all values below LLOQ will be imputed by a random number draw from a uniform distribution in $[0, \text{LLOQ}]$. The minimum computed across all samples will be used if the LLOQ is not provided.
- If more than 50% of samples have values below LLOQ, the biomarker will be discarded from statistical analyses
- If the percentage of values below LLOQ is between 25% and 50%, it will be checked if the values below LLOQ occur mostly in a specific study group. The Fisher test will be used to check the dependency between the occurrence of below LLOQ and group.
- The biomarker will be discarded from statistical analysis if the LLOQ occurrence is group independent. Values below LLOQ will be imputed by the minimum computed across all samples, otherwise.

Missing values not due to measurements being below LLOQ maybe be imputed by the mean value computed across all samples, as appropriate.

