1.3.3 Efficacy endpoints

Primary efficacy endpoint is percent change from baseline in TEWL after 5 STS assessed on lesional skin at Week 15 in AD patients.

Secondary efficacy endpoints are:

- Change (percent and absolute) from baseline in TEWL after 20 STS (after 15 STS, after 10 STS) assessed on:
 - Lesional/non-lesional skin at Week 16 in AD patients
 - Normal skin at Week 16 in healthy volunteers
- Change (percent and absolute) from baseline in TEWL after 5 STS assessed on:
 - Non-lesional skin at Week 16 in AD patients
 - Normal skin at Week 16 in healthy volunteers
- Change (percent and absolute) in TEWL before STS (after STS) on:
 - Lesional/non-lesional skin in AD patients over time
 - Normal skin in healthy volunteers over time
- Change (percent and absolute) in TEWL AUC (a composite measure before and after 5, 10, 15, and 20 STS) for skin barrier function in:
 - Lesional/non-lesional skin in AD patients over time
 - Normal skin in healthy volunteer over time

Tertiary (Exploratory) efficacy endpoints are:

- Change (percent and absolute) in lipidomics parameters in lesional and non-lesional skin including the ratio of EOS CER and NS CER, and FLG breakdown products of UCA and PCA concentrations over time.
- Global characterization of protein-bound CER over time.
- Change (percent and absolute) in the expression of proteins associated with skin barrier function including keratin intermediate filaments, proteins associated with inflammatory response, and glycolysis and oxidative stress response proteins in STS protein extracts over time.
- Change (percent and absolute) in epidermal hypertrophy parameters including epidermal thickness (μm), superficial plexus depth (μm), blood vessel diameter (μm) and density (segments/mm²) measured by OCT over time.
- Change (percent and absolute) in stratum corneum lipid structure measured by FTIR spectroscopy in conjunction with tape-stripping over time.
- Changes in expression of genes associated with epidermal differentiation, barrier and lipid metabolism, and Type 2 inflammation over time.
- Change (percent and absolute) in CDLQI over time.
- Change (percent and absolute) in EASI over time.
- Change (percent and absolute) in ISS for target lesion over time.
- Change (percent and absolute) in POEM over time.

- Change (percent and absolute) in assessment of worst itch NRS over time.
- Change (percent and absolute) in sleep disturbance NRS over time.
- Change (percent and absolute) in skin pain NRS over time.

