2.1.2.2 Outlier detection

Biomarker will be investigated for outliers regardless of group or visit. A value will be declared outlier if it falls out of the interval $[Q1-3*IQR, Q3+3*IQR]$, where Q1 denotes the first quartile,

Q3 the third quartile and IQR the interquartile range. Outliers will be imputed by $Q1-3*IQR$ and $Q3+3*IQR$, respectively. Samples will be investigated for possible contamination that may lead to sample being outlier. For this purpose, samples boxplots, principal component analyses (PCA) hierarchical cluster dendrogram will be used. Outlier samples will be scrutinized and maybe discarded from the statistical analyses.

The distribution of biomarkers will be assessed by histogram and QQ-plot. The values may be log-transformed to fit a Gaussian distribution prior to some statistical analyses. The standardization may be performed for multivariate analyses.

2.1.2.3 *Batch effect assessment*

Samples maybe analyzed or transferred to NJH in different batches. PCA will be computed and a visual inspection of the projection of the samples on the first principal components will enable a first view of the potential batch's effect. The batch effect will be assessed using a linear model estimating a batch effect for each biomarker. This model will include the batch effect, the visit, the health status and interaction between visit and health status. The relevance of the correction for batch effect will be assessed by the p-values of the batch effect.

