2.2.2 Data Visualization

Spaghetti plots

The biomarker profiles will be represented graphically using line plots (one line per subject). The lines will be colored by group. Additional plots will be generated by age categories as appropriate.

Profile plots

For each biomarker, the mean \pm SEM will be represented graphically by group and by visit for the absolute values and percent change from baseline. Additional plots will be generated by age categories as appropriate.

Boxplots

Longitudinal boxplots for absolute values will be provided by group and by visit. Additional plots will be generated by age categories as appropriate.

Heatmaps

A heatmap representation will be provided for each biomarker data matrix highlighting the 2 study groups (AD lesional, non-lesional and healthy volunteers) and different study visits. The age categories will be represented as appropriate. Biomarkers will be clustered according to an unsupervised clustering on Pearson correlation with Ward's agglomeration technique and a dendrogram will be added to the map. Each biomarker will be centered to the mean and reduced to the unit standard deviation. To improve the readability a separate heatmap will be generated with only the baseline biomarker levels and different groups will be highlighted.

Principal component plot

PCA plot will be conducted on log-transformed and scaled data for each biomarker data matrix. The data will be visualized on a 2-dimensional plot of first principal component (PC1) versus PC2 highlighting potential group differences and change during the study. Confidence ellipses will be added as appropriate. A scatterplot with only the baseline samples may be generated to ease the readability. Depending on the percentage of variability explained on the PC1, a second technique for deriving a composite biomarker will be applied.

Median polish

A two-way decomposition (row effect + column effect + overall effect) of the data matrix with each biomarker type will be performed using the Tukey's median polish procedure. The biomarker will be on columns and the samples on rows. The row effect will be extracted as composite biomarker.

Composite biomarker

PC1 and the row effect from the median polish algorithm will be analyzed as composite biomarkers analog to single biomarker. This includes the correlation with TEWL values, the difference between the study groups and the change during the study.

MDS and t-SNE

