2.5 IDENTIFICATION OF BIOMARKERS

2.5.1 Differentially expressed biomarkers

The biomarker potentially linked to the disease status (lesional, non-lesion or healthy skin) and the biomarker changing with the treatment will be identified using a linear mixed model. For each biomarker, the following model will be used to test for any interaction between group and visit for group i, visit j and subject k:

$$y_{ijk} = \mu + \text{group}_i + \text{Visit}_j + \text{group}_i \text{Visit}_{ij} + \text{Subj}_k + \varepsilon_{ijk}$$

with group, visit and interaction between group and visit considered as fixed effects and subject as random effect. Baseline will be used as reference visit and healthy skin as reference group. The data will be log-transformed. A contrast matrix will be defined for extracted the comparison of interest such as group difference at baseline or at Week 16. The fold-changes will be derived, and volcano-plots will be provided as appropriate. The intersection between biomarker differentially expressed at baseline between lesional vs. non-lesional, lesional vs healthy skin and non-lesional vs. healthy skin will be represented graphically using Venn diagrams. The proportion of biomarker changing significantly from baseline to Week 16 will be derived for each study group. The direction of the changes will be highlighted.

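### Biomarker SAP 2.1.2.1: a single uniform draw for each value below LLOQ makes log-scale estimates and mean percent change depend on the random seed

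*SAP*

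**What the plan says.** Section 2.1.2.1 of the biomarker SAP handles values below LLOQ in three branches, according to their share among all samples of a biomarker.

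- Under 25%: "If for a given biomarker, less than 25% of all samples have values below LLOQ", then "all values below LLOQ will be imputed by a random number draw from a uniform distribution" running from 0 to LLOQ.
- 25% to 50%: a Fisher test checks whether the low values depend on group. If they do not, the biomarker is dropped. "Values below LLOQ will be imputed by the minimum computed across all samples, otherwise".
- Above 50%: "If more than 50% of samples have values below LLOQ, the biomarker will be discarded from statistical analyses".

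Only the first branch involves a random draw. The section states no seed, repeated draws, lower bound above 0 or sensitivity analysis for it.

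The completed data then serve two separate purposes. For the mixed model in section 2.5.1, which yields the fold changes, "The data will be log-transformed", without condition. For the profile plots in section 2.2.2, mean ± SEM "will be represented graphically by group and by visit for the absolute values and percent change from baseline". Section 1.3.3 also lists "Change (percent and absolute) in lipidomics parameters in lesional and non-lesional skin" among the exploratory endpoints, with similar entries for filaggrin breakdown products and protein expression.

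**The concern.** A uniform draw that may fall anywhere down to 0 suits neither use. Logging turns draws near 0 into a long left tail that reflects the imputation rule and not the assay. Dividing by such a draw can produce a very large percent change for a child in whom nothing changed. Because each value is drawn once, two analysts who follow the text exactly but use different seeds can report different fold changes and very different mean percent-change curves.

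At stake is whether the biomarker results can be reproduced. They are used to describe the treatment effect on skin biomarkers and to identify and rank biomarkers.

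**Working it through.** **Inputs from the SAP.** Draws from U(0, L) with L = LLOQ; the 25% limit; the log-scale model (2.5.1); percent change with mean ± SEM (1.3.3, 2.2.2); 20 evaluable patients (clinical SAP 1.3). The SAP gives no figure of its own to reproduce.

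**Assumed.** Lognormal biomarkers. The documents give no biomarker SD, LLOQ or share below LLOQ, so ranges are shown.

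**Step 1, without distributional assumptions.** For U ~ U(0, L): E[ln U] = ln L - 1, SD(ln U) = 1, and E[1/U] is infinite. One draw in ten falls below L/10. A child with such an imputed baseline and a follow-up value equal to L has a percent change above 100 × (10 - 1) = 900%. This child alone moves a mean over 20 children by more than 900/20 = 45 percentage points.

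**Step 2, one group's log mean and variance, 20% below LLOQ.** Take the true log mean as 0. Then z = -0.842 and φ(z)/0.2 = 1.400.

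*Log SD 0.5.* ln L = -0.421. True values below L average 0.5 × (1.400 - 0.842) = 0.28 below ln L, with SD 0.23; the draws average 1.0 below, with SD 1. Values above L have mean 0.175 and variance 0.146.
- Mean with draws: 0.2 × (-1.421) + 0.8 × 0.175 = -0.144, so the geometric mean is about 13% too low (exp(-0.144) = 0.866).
- Variance: 0.2 × (1 + 1.421²) + 0.8 × (0.146 + 0.175²) - 0.144² = 0.724. Divided by 0.25, this is 2.9 times the truth.

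*Log SD 1.0.* ln L = -0.842; values above L have mean 0.350 and variance 0.583.
- Mean: 0.2 × (-1.842) + 0.8 × 0.350 = -0.088.
- Variance: 0.2 × (1 + 1.842²) + 0.8 × (0.583 + 0.350²) - 0.088² = 1.435, or 1.4 times the truth.

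At 10% below LLOQ and log SD 0.5 the variance ratio is still 2.13.

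**Step 3, the same formulas with a fixed substitute, 20% below LLOQ.**

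| Substitute | Log SD 0.5: bias, variance ratio | Log SD 1.0: bias, variance ratio |
|---|---|---|
| Uniform draw | -0.144, 2.9 | -0.088, 1.4 |
| LLOQ/√2 | -0.014, 1.03 | +0.042, 0.85 |
| LLOQ/2 | -0.083, 1.53 | 0.2 × (0.558 - 0.693) = -0.027, 1.03 |

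**Step 4, only the seed changed.** One fixed data set of 20 pairs; assumed log SD 0.6, within-child correlation 0.5 and true ratio 1.5; 2,000 seeds; 2.5th to 97.5th percentile.

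| Baselines below LLOQ | Mean % change | SEM | Geometric mean ratio | Paired t on logs |
|---|---|---|---|---|
| 1 of 20 | 78 to 696 | 27 to 627 | 1.25 to 1.69 | 0.75 to 2.43 |
| 4 of 20 | 81 to 1651 | 27 to 1525 | 1.20 to 2.04 | 0.55 to 2.73 |

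With 4 of 20, the median percent change ran only from 52 to 63 and the raw baseline mean from 0.99 to 1.07.

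**Step 5, no true change.** 20,000 simulated trials of 20 children; between-child log SD 0.5, within-child 0.2. At 20% below LLOQ the mean percent change has median +21% and 95th percentile about +304%, against +4% and about +15% with the true values. At 5% it has median +6% and 95th percentile +88%. When the frequency below LLOQ is equal at both visits, the mean log change stays centred on 0, but at 20% its SD is 0.18 against 0.06.

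**Step 6, would the outlier rule catch the draws?** The lower fence in section 2.1.2.2 is Q1 - 3 × IQR. For raw lognormal data it is negative when 4·exp(-0.6745 s) < 3·exp(0.6745 s), that is, when the log SD s exceeds ln(4/3)/(2 × 0.6745) = 0.21. Above that, it cannot flag a positive draw, however small. The rule is not stated to apply to derived percent changes.

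**The case against.** The best defence is that the damage is confined.

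- The rule covers only assays with an LLOQ. RNA-seq differential testing works on raw counts.
- All biomarker analyses are declared exploratory, without formal testing (2.6).
- Section 2.2.1 names percent change only for OCT; for lipidomics and proteomics it plans summaries by group and visit, with medians and quartiles. Boxplots are planned too.
- The main model already gives fold changes, and histograms and QQ-plots (2.1.2.2) would show a left tail.
- The larger figures use a 20% share, near the top of the branch, and assumed SDs.

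Most of this stands as a limit on scope. It does not remove the point. The 25% limit is taken over all samples, so a single group and visit can exceed it, and one imputed baseline in 20 is enough for the instability in step 4. Percent change remains a listed endpoint form and a planned mean ± SEM plot. Exploratory status excuses the lack of error control but not results that vary with an arbitrary draw. Recording a seed would make the output repeatable without making the draw less arbitrary. The logging allowed in section 2.1.2.2 ("The values may be log-transformed to fit a Gaussian distribution prior to some statistical analyses") does not repair values already imputed.

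A reader might infer that every mean and error bar depends on the seed, that every fold change is biased, or that percent change is taken on logged values. The documents support none of these. Raw-scale means and median percent change hardly move. A contrast is biased only when the frequency below LLOQ differs between the sides compared. Logging and percent change are separate uses of the same data.

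**Conclusion.** The point holds for the under-25% branch and for two kinds of output: log-scale analyses, and mean percent change with its SEM.

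On the log scale the rule inflates variance, illustrated as 1.4 to 2.9 times at 20% below LLOQ for log SD 1.0 and 0.5. It makes estimates depend on the seed. The -0.144 in step 2 is one group's bias; it carries over in full to a contrast only against a comparator without values below LLOQ. For mean percent change, an imputed baseline means that no finite expected value exists, whatever the biomarker's distribution.

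The sizes rest on assumed lognormal data, SDs and shares below LLOQ. The SD of 1 on the log scale, the infinite mean of 1/U and the dependence on the seed do not. The TEWL endpoints, including the primary one, are unaffected. The rule should be changed before the biomarker data are analysed, because every alternative examined does better at little cost.

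**What to change.** In section 2.1.2.1, replace the uniform draw:

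1. In the log-scale mixed model of 2.5.1, treat values below LLOQ as left-censored in the likelihood.
2. For descriptive outputs, use one pre-specified fixed substitute, for example LLOQ/√2, and repeat with LLOQ/2 as a sensitivity check. The two are not interchangeable: step 3 shows that which is closer depends on the biomarker's spread.
3. In 1.3.3 and 2.2.2, summarise change from baseline as a geometric mean ratio or a median percent change instead of a mean percent change.
4. Keep children whose baseline is below LLOQ and flag them. Leaving them out would select on baseline.

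The cost is a few lines of text, a changed imputation step and slightly more programming for the censored model. A fixed substitute creates ties and leaves some bias. With LLOQ/√2 at log SD 1.0 it also understates the variance (0.85 times the truth).

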1 OVERVIEW AND INVESTIGATIONAL PLAN

1.1 INTRODUCTION

Atopic dermatitis (AD) is a chronic systemic inflammatory skin disease with a prevalence of up to 25% in children and up to 7% in adults. AD is caused by the complex interplay between epithelial dysfunction and dysregulated/over-activated Type 2 immune response in the skin, with a special role for IL-4/IL-13-driven signaling in AD pathogenesis. This Type 2 hyperactivation blocks terminal differentiation of skin keratinocytes and formation of a mature stratum corneum that is mainly responsible for the skin barrier function.

Dupilumab is a human monoclonal antibody that blocks the shared receptor subunit for interleukin (IL) -4 and IL-13, thus inhibiting signaling of both IL-4 and IL-13, cytokines that are key drivers of Type 2 inflammatory diseases. Dupilumab is recently approved in the US for the treatment of pediatric patients ≥ 6 and < 12 years of age with moderate-to-severe AD whose disease is not adequately controlled with topical prescription therapies or when those therapies are not advisable.

The LPS16764 study is an open label exploratory phase 4 study designed for assessing the effect of subcutaneous injection of dupilumab on skin barrier function measured as transepidermal water loss (TEWL) in AD pediatric patients. The effect of dupilumab treatment on skin barrier function is evaluated using TEWL in conjugation with skin lipidomics, proteomics, and transcriptomics generated from skin tape stripping (STS) samples. Skin barrier structure changes is evaluated using optical coherence tomography (OCT) and Fourier-Transform Infrared (FTIR) spectroscopy in both predefined lesional and non-lesional skin areas.

This document provides a statistical analysis plan for all biomarker data repeatedly collected during the LPS16764 study. The term biomarker in this document will then refer to lipidomics, proteomics, transcriptomics, or filaggrin (FLG) breakdown products. TEWL may refer to a measurement before STS; after a given number of STS samplings or can be AUC (area under the curve) of TEWL before STS and after STSs performed at the specified STS visits. The term study group or group in general refers to lesional, non-lesional or normal health skin group. This biomarker statistical analysis plan is based on clinical trial protocol Version 1 (13-Jul-2020).

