1.2 STUDY DESIGN

[figure not shown]
LPS16764 is a Phase 4 open-label, exploratory study in two sites evaluating the effect of dupilumab on skin barrier function in pediatric patients aged between ≥ 6 and < 12 years old with moderate-to-severe AD. A healthy volunteer cohort will be enrolled as a reference comparator matched to AD for age-, gender-, study-site and sampling will be matched on targeted lesion area. Approximately 24 pediatric patients with moderate-to-severe AD will be enrolled to achieve 20 evaluable patients. These enrolled AD patients will receive Investigational medicinal product (IMP) dupilumab treatment during the study. Approximately 24 healthy volunteers will be enrolled to achieve 20 evaluable subjects. These enrolled healthy volunteers will not receive any IMP treatment during the study.

The maximum study duration per participant will be 32 weeks. The study will comprise of:

- Screening period 1 (Day -28 to Day -1): Participants will be evaluated according to
- Inclusion and exclusion criteria.
- Baseline visit (Week 0, Day 1): Participants who remain eligible will be enrolled.
- A 16-week treatment phase for AD patients and a 16-week observation period for healthy volunteers.
- A 12-week follow-up period.

Biomarker assessment based on lipidomics, proteomics, and transcriptomics in STS samples will be conducted at baseline (Week 0, Day 1), Week 2, Week 4, Week 8, Week 12, EoT at Week 16, and Follow-ups at Week 22 and Week 28.

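### The biomarker LLOQ rule discards any marker more than 50% below LLOQ across pooled samples, without the skin-group check it applies at 25–50%, so markers quantifiable in one skin group only are lost

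*SAP*

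**What the plan says.** The rule is in section 2.1.2.1 of the biomarker SAP. Section 1.1 sets its scope: "The term biomarker in this document will then refer to lipidomics, proteomics, transcriptomics, or filaggrin (FLG) breakdown products".

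Section 2.1.2.1 first announces that, for each biomarker, "the number of values below LLOQ will be computed by group (lesional, non-lesional and healthy skin"). The cut-offs that follow use the share of all samples, not these counts by group:

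- **Under 25% below LLOQ:** the values are replaced by a uniform random draw between 0 and the LLOQ.
- **25% to 50%:** "it will be checked if the values below LLOQ occur mostly in a specific study group", using a Fisher test. A group-independent marker is discarded. For a group-dependent one, "Values below LLOQ will be imputed by the minimum computed across all samples, otherwise".
- **Over 50%:** "If more than 50% of samples have values below LLOQ, the biomarker will be discarded from statistical analyses". No condition is attached.

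Genes have a separate filter under Transcriptomics in section 2.1.1. It is applied to the healthy and AD cohorts separately: "Genes that successfully pass the filter in at least one data set will be kept".

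The purpose of the data is given in section 2.5.1: "The biomarker potentially linked to the disease status (lesional, non-lesion or healthy skin) and the biomarker changing with the treatment will be identified". Section 2.5.2 then looks for markers that discriminate between the three skin groups.

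**The concern.** In the 25–50% band the plan treats non-detection that depends on skin group as information and keeps the marker for that reason. Above 50% it abandons the principle. With three groups of similar size, which side of 50% a clear group pattern falls on depends on its direction. Presence in one group and absence in two falls above the line; absence in one and presence in two falls below it. The two patterns separate the groups equally well, yet one is discarded unchecked and the other is kept.

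At stake is whether some of the markers that differ most between lesional, non-lesional and healthy skin reach the group comparison at all. Pooling over visits adds to this. A marker that appears in lesional skin at only some visits, as one responding to treatment might, is further diluted.

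**Working it through.** **Inputs**

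- Patients: about 24 enrolled for 20 evaluable (biomarker SAP 1.2). Each gives a lesional and a non-lesional sample at an STS visit.
- Healthy volunteers: "Approximately 24 healthy volunteers will be enrolled to achieve 20 evaluable subjects" (biomarker SAP 1.2). Each gives one sample per visit.
- Drop-out: 15% (clinical SAP 1.3). Check of the plan's own figure: 20 / (1 − 0.15) = 23.5, rounded up to 24. It reproduces.
- STS visits: eight in biomarker SAP 1.2 (Weeks 0, 2, 4, 8, 12, 16, 22, 28). The number of visits cancels from the shares if attendance is similar across groups.

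**Step 1. Pooled share below LLOQ.** With P patients and H volunteers, each visit gives 2P + H samples. A marker quantifiable in one group of size g only has a share below LLOQ of 1 − g / (2P + H). A marker absent in that group only has a share of g / (2P + H).

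| P / H | Samples per visit | Only lesional quantifiable | Only healthy quantifiable | Absent only in lesional | Absent only in healthy |
|---|---|---|---|---|---|
| 20 / 20 | 60 | 66.7% | 66.7% | 33.3% | 33.3% |
| 20 / 24 | 64 | 68.8% | 62.5% | 31.2% | 37.5% |
| 24 / 20 | 68 | 64.7% | 70.6% | 35.3% | 29.4% |

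Non-lesional skin gives the same figures as lesional skin, and 24 / 24 the same as 20 / 20. Every one-group marker is over 50% and is discarded. Every marker absent in one group lies between 25% and 50% and goes to the Fisher test.

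**Step 2. How far the pattern can soften.** If one group is fully quantified, the marker is discarded once average detection in the other two falls below (0.5 × total − g) / (total − g). With 20 per group this is (30 − 20) / 40 = 25%. Over the cohort sizes above it ranges from 20.0% to 29.2%.

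**Step 3. What the Fisher check would have found.** These are exact 2 × 3 tests that treat samples as independent, so they show direction only.

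- One visit, 20 per group, quantified in all samples of one group and none of the others: p = 7.2e-16. The marker absent in one group only gives the same p-value. The first is discarded untested; the second is tested and kept.
- Eight visits, 160 samples per group, below LLOQ in 16, 109 and 109: 234/480 = 48.75%, p = 2e-35, kept.
- Eight visits, below LLOQ in 16, 115 and 115: 246/480 = 51.25%, p = 9e-40, discarded.

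**Step 4. Pooling over visits.** A marker quantifiable in all lesional samples at three of eight visits and nowhere else is quantified in 3 × 20 = 60 of 480 samples. It is 87.5% below LLOQ and is discarded.

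**Step 5. The gene filter.** A gene is dropped if it is under 1 cpm in more than half of the samples of both cohorts. The AD cohort pools lesional and non-lesional skin. For a gene absent from non-lesional and healthy skin:

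- 95% lesional detection: (5% + 100%) / 2 = 52.5% low in AD.
- 90% lesional detection: (10% + 100%) / 2 = 55% low in AD.

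Both are over half, and the healthy cohort is 100% low, so the gene is dropped. At 100% lesional detection the AD share is exactly 50% and the gene survives. The filter protects a healthy-only gene but not reliably a lesional-only one.

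**The case against.** The strongest defence is that a pooled cut-off has a purpose. Retained markers also enter heatmaps, principal components, median polish, clustering, elastic net and random forest (biomarker SAP 2.2.2, 2.3, 2.5.2, 2.5.3). There, a marker that is two-thirds imputed adds mostly noise or a constant. Its fold change is set largely by the imputed value. This stands. It argues for keeping such markers out of those analyses, not for omitting a comparison of detection rates.

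It can also be said that the counts by group are computed for every biomarker before any discard, so the pattern is not necessarily invisible. That is correct, but the plan draws no consequence from those counts above 50%.

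Three stronger readings are tempting and are not supported:

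- **Genes are fully protected while other markers are not.** Step 5 shows that the gene filter is only a partial safeguard.
- **The rule should be to discard only markers mostly below LLOQ in every skin group.** That would also rescue group-independent markers, such as one 40% below LLOQ in all three groups, which the plan deliberately drops. It would still lose the marker in Step 4, which is 62.5% below LLOQ even in lesional skin.
- **The imputed minimum biases fold changes by a known amount.** The plan does not say whether the minimum is the lowest quantified value or the lowest reported one. Any size would rest on assumed distributions, and the choice among imputation values is largely preference. What remains is that the term needs a definition.

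**Conclusion.** The point holds as a cheap improvement. Across the cohort sizes the plan allows for, a lipid, protein or FLG breakdown product quantifiable in one skin group only is always discarded (62.5–70.6% below LLOQ). One absent in a single group only (29.4–37.5%) is tested and kept. This is inconsistent with the plan's own treatment of group dependence and with the aims of sections 2.5.1 and 2.5.2.

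It rests on two assumptions. First, the 50% is read as a share of samples pooled across groups and visits; the under-25% rule refers expressly to all samples, and no visit restriction is given. Second, the three groups contribute similar numbers of samples, as the design implies.

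A reader might infer that important markers will be lost, or that the trial's main result is affected. Neither follows. The plan gives no LLOQ rates, so no given marker can be shown to cross 50%. The biomarker analyses are exploratory without formal testing (section 2.6), and the TEWL primary endpoint does not depend on this rule.

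**What to change.** In section 2.1.2.1:

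1. Apply the existing Fisher group check to markers above 50% below LLOQ as well. Discard those found group-independent, and leave the discard of group-independent markers at 25–50% unchanged.
2. For group-dependent markers above 50%, report and compare detection rates by skin group (quantified yes or no) as the main result. Keep these markers out of the principal component, clustering and elastic-net analyses. Mark any fold change as dependent on the imputed value.
3. State whether the minimum used for imputation is the lowest quantified value.

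The cost is a few sentences of wording and a short code change, using counts the plan already produces. A few more markers are carried forward. The Fisher p-values ignore repeated samples and paired skin areas from the same child, so they should serve only as a sorting rule.
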